#### 8.1.4

#### Recording Adverse Events

Patients should be instructed to report any AE that they experience to the investigator. Investigators should assess for AEs at each visit. Adverse events occurring during the clinical study and the follow-up period should be recorded in the eCRF. To capture the most potentially relevant safety information during a clinical study, it is important that investigators record accurate AE terms in the eCRF.

In addition to the above AEs, patients will be instructed to report any changes in skin or vision in order to assess possible phototoxicity of NS-018. During the periodic safety monitoring, investigators should be reminded to inquire of the patients about any changes in their skin or vision.

Investigators are required to document all AEs occurring during the clinical study, commencing with the first dose of NS-018 and including the protocol-defined post-treatment follow-up period in the eCRF. The AEs occurring following the signature of the informed consent, but prior to the first dose of NS-018 will not be reported as AEs unless the event is related to a study procedure. This information (events occurring following the signature of the informed consent but prior to the first dose of NS-018, and not related to a study procedure) will be collected within the medical history section of the eCRF. It is

also important to record all AEs that result in permanent discontinuation of NS-018, whether serious or non-serious.

All AEs occurring after any administration of NS-018 will be followed until the event resolves, until the event is judged stable and not expected to resolve completely, or until the patient begins alternative treatment.

All AE reports should contain a brief description of the event, date and time of onset, date and time of resolution, intensity, treatment required, relationship to study drug, action taken with the study drug, outcome, and whether the event is classified as serious.

## **8.2 Serious Adverse Event Reporting - Procedure for Investigators**

### **Initial Reports**

All SAEs occurring from the time of the administration of the first dose of study drug until 30 days following the last administration of study drug must be reported to PAREXEL **within 24 hours** of the knowledge of the occurrence (this refers to any AE that meets any of the aforementioned serious criteria). Serious AEs that the investigator considers related to study drug occurring after the 30-day follow-up period will also be reported to PAREXEL. Events that occur after signing consent that are considered related to a required study procedure will also be captured as AEs/SAEs.

To report the SAE, fax the completed SAE report form to PAREXEL (fax number listed below) within 24 hours of awareness. PAREXEL safety personnel are available for SAE reporting on a 24-hour basis. Reports are reviewed during normal business hours.

Safety Contact Information:  
PAREXEL International  
[name]  
[name]

SAE Contact Information:

PPD

Serious AEs should be reported to the reviewing Institutional Review Board (IRB) according to individual requirements. A copy of that report must be retained at the investigative site and filed in the investigator Site File.

The sponsor will notify FDA and all participating investigators in an IND safety report of any adverse experience associated with the use of the drug that is both serious and unexpected or of potentially serious risks from clinical trials or any other source, as soon as possible, but no later than 15 calendar days after the

sponsor receives the safety information and determines that the information qualifies for reporting.

#### Follow-Up Reports

The investigator must continue to follow the patient until the SAE has subsided, or until the condition becomes chronic in nature, stabilizes (in the case of persistent impairment), or the patient dies. Within 48 hours of receipt of new information, the updated follow-up SAE report form, along with any supporting documentation (e.g., laboratory test reports, patient discharge summary, or autopsy reports), should be faxed to PAREXEL clinical safety personnel.

### **8.3**

#### ***Exposure In Utero During Clinical Studies***

The sponsor has a responsibility to monitor the outcome of pregnancies where there has been maternal exposure to the study drug.

Pregnancy alone is not regarded as an AE unless there is a suspicion that the study drug may have interfered with the effectiveness of a contraceptive medication.

Elective abortions without complications should not be handled as AEs, unless they were therapeutic abortions (see below). Hospitalization for normal delivery of a healthy newborn should not be considered a SAE.

All pregnancies must be reported by the investigator to the sponsor on the initial pregnancy report form within 24 hours after becoming aware of the pregnancy. The investigator must follow up and document the course and the outcome of all pregnancies even if the patient was discontinued from the study or if the study has finished.

All outcomes of pregnancy must be reported by the investigator to the sponsor on the pregnancy outcome report form within 30 days after he or she has gained knowledge of the normal delivery or elective abortion.

Any SAE that occurs during pregnancy (including SAEs occurring after last administration of study drug) must be recorded on the SAE report form (e.g., maternal serious complications, spontaneous or therapeutic abortion, ectopic pregnancy, stillbirth, neonatal death, congenital anomaly, or birth defect) and reported within 24 hours in accordance with the procedure for reporting SAEs.

If a female partner of a male study patient who has been exposed to the study drug becomes pregnant, the pregnancy and outcome of pregnancy should be monitored.

### **8.4**

#### **Laboratory Assessments**

Safety laboratory assessments (hematology, chemistry, and urinalysis) will be performed locally at each center's laboratory by means of their established

methods. Before starting the study, the investigator will supply the sponsor with a list of the normal ranges and units of measurement.

## 8.5

### Vital Signs

The following vital signs will be assessed in accordance with the Schedule of Procedures (Appendix A):

- Blood pressure (systolic and diastolic; mmHg);
- Heart rate (beats per minute);
- Body temperature (°C, oral);
- Respiration rate (breaths per minute).

## 8.6

### Electrocardiograms

To determine whether NS-018 causes prolongation of the QTc interval, 12-lead ECG tracings will be collected as outlined below from all patients treated with NS-018:

- Screening (locally read for eligibility determination; centrally read for analysis);
- Cycle 1 Day 1: pre-dose and 2, 4, 6, and 8 hours after administration of NS-018; centrally read;
- Cycle 1 Day 8 (Phase 1 and Phase II), Cycle 1 Day 15 (Phase 2): pre-dose and 2 hours after administration of NS-018; centrally read;
- Cycle 2 Day 1: pre-dose and 2 hours after administration of NS-018; centrally read; and
- Cycle 3 Day 1, Cycle 4 Day 1, Cycle 7 Day 1 and every 3 cycles thereafter and End of Study: pre-dose; locally read.

All ECGs up to Cycle 13 will be taken in triplicate about 1 minute apart and the median QTc value will be evaluated at the respective study site for inclusion criterion 10 (Section 4.1), for compliance with study protocol-defined procedures and safety. After Cycle 13, all ECGs will be single reading only.

When time points for ECG measurements coincide with the time points for pharmacokinetic sampling, triplicate ECG collection should take place immediately prior to the collection of the plasma sample for pharmacokinetics.

All ECGs will be read locally and/or centrally. The ECGs for central reading will be sent after local reading; transmission will not be done immediately.

Details regarding the ECG collection and reading will be provided in the study reference manual.

Following the analysis of the PK data from the first cohort of patients, the ECG schedule may be modified so that tracings are taken around the time of peak plasma concentrations.

## 8.7

### Physical Examinations

Physical examinations, including weight and spleen size, will be performed in accordance with the Schedule of Procedures (Appendix A).

**9**

**EFFICACY ASSESSMENTS**

**9.1**

**Treatment Response**

Efficacy will be assessed using the IWG-MRT during the Phase I portion of the study and IWG-MRT and ELN during the Phase II portion of the study. The criteria are provided in Appendix I.

**9.2**

**Spleen Size Assessment**

In the Phase 1 portion of the study, spleen size will be assessed clinically, by palpation.

In Phase 2, spleen size will be assessed by palpation and by MRI (CT scan for patients not able to tolerate MRI), which will be transmitted to the central reading center and read centrally. Details regarding the MRI/CT protocol will be provided in the study reference manual.

**9.3**

**Bone Marrow Assessment**

Bone marrow will be assessed by aspiration and biopsy, according to standard practice at the site.

**10**

**PHARMACODYNAMIC AND PHARMACOKINETIC ASSESSMENTS**

Instructions for the processing, handling, and shipment of samples for central analysis will be provided in the study reference manual.

**10.1**

**Pharmacodynamic Assessments**

10.1.1

**JAK2 V617F Allele Burden Assessment**

The intended time points for JAK2 V617F allele burden assessment in both the Phase 1 and Phase 2 portion of the study are specified below.

- Cycle 1 Day 1: pre-dose;
- Cycle 2 Day 1: pre-dose (if mutation present prior to start of therapy);
- Cycle 4 Day 1: pre-dose (if mutation present prior to start of therapy); and
- Cycle 7 Day 1 and every 3 cycles thereafter: pre-dose (if mutation present prior to start of therapy).

10.1.2

**Phospho-STAT3 Assessment**

The intended time points for Phospho-STAT3 assessment are specified below for each phase of the study.

**Phase 1:**

- Cycle 1 Day 1: pre-dose and approximately 3 and 6 hours after administration of NS-018 ;
- Cycle 1 Day 8: pre-dose and approximately 3 and 6 hours after administration of NS-018 ;

- Cycle 2 Day 1: pre-dose and approximately 3 and 6 hours after administration of NS-018 ;

**Phase 2:**

- Cycle 1 Day 1: pre-dose and approximately 2 and 3 hours after administration of NS-018 ;
- Cycle 1 Day 15: pre-dose and approximately 2 and 3 hours after administration of NS-018 ;
- Cycle 2 Day 1: pre-dose and approximately 2 and 3 hours after administration of NS-018 ;

**10.1.3 Cytokine Assessment**

The intended time points for cytokine assessment in both the Phase 1 and Phase 2 portions of the study are specified below.

- Cycle 1 Day 1: pre-dose
- Cycle 2 Day 1: pre-dose
- Cycle 3 Day 1: pre-dose
- Cycle 4 Day 1: pre-dose

Additional analysis of excess plasma PD samples may be performed for other pharmacodynamic marker evaluations.

**10.2 Pharmacokinetic Assessment**

Blood samples will be obtained for PK assessments to analyze NS-018 and its metabolites. The intended time points are specified below for each phase of the study.

**Phase 1:**

- Cycle 1 Day 1: pre-dose and approximately 0.5, 1, 2, 3, 4, 6, 8, and 24 hours after administration of NS-018;
- Cycle 1 Day 8: pre-dose and approximately 0.5, 1, 2, 3, 4, 6, and 8 hours after administration of NS-018; and
- Cycle 2 Day 1: pre-dose and approximately 0.5, 1, 2, 3, 4, 6, 8, and 24 hours after administration of NS-018.

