**6 TREATMENT AND RESTRICTIONS**

**6.1 Treatment**

**6.1.1 Treatment Regimen, Dosage, and Duration**

Patients will be treated at the dose cohort level to which they are assigned. All study drug will be self-administered orally. NS-018 will be self-administered 2 hours or more after the last meal and at least 1 hour before the next meal.

The dose levels planned and the numbers of patients in each dose level are presented below.

Once Daily (QD) Cohort [completed]			Twice Daily (BID) Cohort							
Cohort	NS-018 Total Daily Dose(mg)	No. of Patients Per Cohort	Cohort	NS-018 Total Daily Dose(mg)	No. of Patients Per Cohort					
Phase 1			Phase 1							
QD 1#	75	3-6								
QD 2#	125	3-6								
QD 3#	200	3-6	BID 1#	200 (100×2) £	3-6					
QD 4#	300	3-6		—	—					
	—	—	BID 2#	400 (200×2) £	3-6					
	—	—	BID 3#	600 (300×2) £	3-6					
	—	—	BID 4#§	800 (400×2) £	3-6					
Phase 2	MTD or lower Up to 20 patients									
MTD = maximum tolerated dose.										
£ BID dosing must be administered 12 hours apart										

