# If a DLT is experienced at any dose level, an intermediate cohort at a lower dose may be considered, as recommended by Safety Review Committee										
§ Additional cohorts at doses > 400 mg BID (800 mg/day) may be considered by the Sponsor if agreed by the Safety Review Committee after review of PK, PD, and safety data. The maximum planned increase in dose between cohorts will be 200 mg as the total daily dose (e.g., the dose level above 400 mg BID will not exceed 500 mg BID )										

During the study, a Safety Review Committee will review data from each cohort and may make dosing schedule changes based on the data review. The Safety Review Committee is described in detail in Section 13.9.

In the Phase 1 portion of the study, sequential cohorts of 3 to 6 patients will be treated with escalating doses until the MTD is established (see Section 6.1.1.3). The first patient in each cohort must be observed for at least 7 days of dosing with NS-018. If there is no clinically significant toxicity observed in that patient, enrollment in the cohort may continue. If a significant toxicity occurs, including any possible dose-limiting toxicity (DLT, see Section 6.1.1.2), the Safety Review Committee must meet and determine whether additional patients may be entered at that dose or an intermediate cohort at a lower dose should be considered. Each cohort can be assessed after at least 3 patients have completed 28 days of study drug dosing.

The Safety Review Committee can make dosing schedule changes (twice daily dosing rather than once daily dosing; intermediate dose levels if toxicity occurs that does not rise to the level of a DLT) based on pharmacodynamic, pharmacokinetic, and safety review. If twice daily dosing requires evaluation, dosing would start at one total daily dose level below the last once per day dose level that was declared safe. For example, when 300 mg QD was declared safe,

the starting dose for BID dosing would be 100 mg twice daily, 12 hours apart [representing a total daily dose 200 mg]).

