#### 6.1.2 Compliance Control

Patient compliance will be monitored by assessing the tablet count from the drug packages returned at each visit. Patients will complete a study drug dosing diary daily that will document the time of day they took their study drug. Tablet counts will be compared by the site to the dosing diary to further assess compliance and aid patient education regarding compliance. Documentation on the electronic Case Report Form (eCRF) will account for patient compliance during each cohort. Patients will be instructed to return any unused study drug and packaging when attending clinic visits or if the patient is discontinued before the study is complete.

Patients who take  $<80\%$  of the expected prescribed regimen will be counseled on the importance of taking the study drug appropriately. If compliance is  $<80\%$  during the first month of therapy, the patient will be counseled, remain on study drug and will follow the study assessment schedule. The patient will be included in all final study analysis populations (See Section 12.2), however the patient will not be included in the data from each cohort that is reviewed by the Safety Review Committee to determine dosing schedule changes. In the event that a patient's compliance is  $<80\%$  during the first month of therapy, an additional patient will be enrolled in the cohort and their data will be included in the cohort review by the Safety Review Committee as well as in all final study analysis populations.

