## **12 STATISTICS**

Additional statistical analyses, other than those described in this section, may be performed if deemed appropriate. A description of the statistical analysis performed on the study data will be outlined in the Statistical Analysis Plan.

Each phase of this study will be analyzed separately. All tables, figures and listings will therefore be separated by study phase.

Interim analyses of PK, PD, and safety data from the Phase 1 portion of the study will be conducted after the MTD has been established.

An analysis of all existing PK, PD, and safety data from the Phase 2 portion of the study will be conducted 6 months after the last patient is enrolled in this part of the study.

The complete analysis of all study data will be contained in the clinical study report at the end of the study.

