## **12.6**

### **Pharmacokinetic Analyses**

Blood samples for PK analysis of NS-018 and its metabolites will be collected at designated study visits. All PK analyses will be based on the PK population.

Plasma concentrations of NS-018 and its metabolites will be summarized descriptively by dose level and time point of collection. Summary statistics including number of patients, arithmetic mean, geometric mean, geometric CV, standard deviation, minimum, maximum, median, coefficient of variation, and standard error of the mean will be presented. Individual patient and mean plasma concentrations of NS-018 and its metabolites will be plotted vs. time in linear and log-linear scale.

Derived PK parameters will be listed and summarized using the same measures as for the plasma concentrations of NS-018 and its metabolites.

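### Does the 24-hour PK sample, which follows a second dose in twice-daily patients, spoil the planned half-life and AUC?

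*Combined protocol and SAP*

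**What the plan says.** Section 10.2 sets the PK times. For Phase 1 the list reads "Cycle 1 Day 1: pre-dose and approximately 0.5, 1, 2, 3, 4, 6, 8, and 24 hours after administration of NS-018", with the same times at Cycle 2 Day 1 and no 24 h sample at Cycle 1 Day 8. Phase 2 has a 24 h sample at Cycle 1 Day 1 only. Appendix A (Phase 1 footnote i, Phase 2 footnote j) agrees. The exceptions are by visit, never by regimen.

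The dose table in Section 6.1.1 marks the once-daily (QD) cohorts as completed and plans four BID cohorts of 3 to 6 patients. Its footnote says "BID dosing must be administered 12 hours apart"; Section 7.3 instead sets 12 hours as a minimum.

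Section 10.2 lists Cmax, Tmax, AUC, terminal half-life and accumulation ratio R as the parameters. Section 12.6 says "Plasma concentrations of NS-018 and its metabolites will be summarized descriptively by dose level and time point of collection" and "Individual patient and mean plasma concentrations of NS-018 and its metabolites will be plotted vs. time in linear and log-linear scale". Section 12 adds: "A description of the statistical analysis performed on the study data will be outlined in the Statistical Analysis Plan". Section 6.1.2 supplies the dose times: "Patients will complete a study drug dosing diary daily that will document the time of day they took their study drug".

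**The concern.** The schedule suits once-daily dosing, where 24 h is the end of the dosing interval and a good late point for the terminal slope. Under BID dosing the same clock time comes after another dose. No text withholds the second dose on PK days, adds a sample just before it, or gives BID its own list.

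Two consequences are possible. First, a BID table or mean curve by time since the morning dose shows a 24 h value that comes mostly from the second dose and can look like a slow tail of the first. Second, a default terminal fit through the last three samples (6, 8 and 24 h) would give a half-life that is far too long and an inflated first-dose AUC.

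PK is a secondary objective in both phases. The Safety Review Committee looks at PK with PD and safety data when it considers schedule changes or cohorts above 400 mg BID. The planned Phase 1 BID cohorts hold 4 × 3 = 12 to 4 × 6 = 24 patients, so the affected group is not small.

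**Working it through.** **Inputs.** From the documents: sampling times (Section 10.2) and BID spacing of 12 h, or at least 12 h (Sections 6.1.1 and 7.3). Assumed, because no human half-life or absorption rate is given: one compartment, half-life *h* of 2, 3, 4 or 6 h (8 and 12 h as sensitivity), absorption rate 0.8 to 3 per h, doses at 0 and 12 h, and the 24 h sample drawn before the next morning's dose. The plan states no figure on this point to reproduce.

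**1. Timeline.** 24 − 12 = 12 h after dose 2, or less if the spacing is longer. The last sample that reflects dose 1 alone is at 8 h. The two wordings on spacing must be reconciled for their own sake, but under either one the 24 h sample follows dose 2.

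**2. Share of the 24 h value due to dose 1.** Once absorption is complete, dose 1 leaves an amount proportional to 2^(−24/h) and dose 2 an amount proportional to 2^(−12/h). The total relative to dose 1 alone is 1 + 2^(12/h).

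| h (h) | 1 + 2^(12/h) | Dose 1 share |
|---|---|---|
| 2 | 1 + 64 = 65 | 1.5% |
| 3 | 1 + 16 = 17 | 5.9% |
| 4 | 1 + 8 = 9 | 11% |
| 6 | 1 + 4 = 5 | 20% |

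The largest ratio goes with the smallest concentration: at h = 2 the 24 h value is only about 2 to 5% of Cmax.

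**3. If the sample were used as first-dose data.** Example with h = 4 and absorption complete. The values at 6, 8 and 24 h are 2^(−1.5) = 0.3536, 2^(−2) = 0.25 and 2^(−6) + 2^(−3) = 0.1406. Their logs are −1.0397, −1.3863 and −1.9617. The times have mean 38/3 = 12.667, so the deviations are −6.667, −4.667 and 11.333, with sum of squares 194.67.

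Slope = (6.9315 + 6.4694 − 22.2321)/194.67 = −0.04537 per h. Half-life = 0.6931/0.04537 = 15.3 h, against a true 4 h.

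The full model at an absorption rate of 1.5 per h gives 6.7, 10.5, 15.3 and 31.8 h for true values of 2, 3, 4 and 6 h. Over rates of 0.8 to 3, half-life is about 3.3 to 5.5 times true and first-dose AUC to infinity about 1.2 to 3.3 times true. R from AUC over 0–24 h through that sample is 0 to 8% low against the 12 h accumulation ratio. Cmax, Tmax and all values up to 8 h do not change.

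At longer half-lives the misuse gives itself away. At 8 h the fit returns 82 to 87 h. At 12 h the 24 h value (2^(−2) + 2^(−1) = 0.75) exceeds the 8 h value (2^(−8/12) = 0.63), the slope is positive and there is no half-life.

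**4. If the sample is left out.** A fit to 4, 6 and 8 h gives half-life 1.00 to 1.16 times true for h of 2 to 6 h, the upper end at slow absorption. First-dose AUC to infinity is about 0.98 to 1.07 times true.

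**5. What the plan directs.** Section 12.6 asks for concentrations by collection time and for plots against time. A 24 h concentration in a BID patient, reported as such, is correct. No section assigns the sample to the terminal fit or to first-dose AUC.

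**6. Pooling of regimens.** 200 mg/day appears both as a QD cohort and as 100 mg twice daily, so a summary by *dose level* might seem to merge them. The term is used both ways in one sentence of Section 6.1.1: "dosing would start at one total daily dose level below the last once per day dose level that was declared safe". Elsewhere that section attaches the term to a BID dose and has DLTs at a dosing schedule evaluated separately. The dose table lists the two cohorts apart. Merging is not prescribed.

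**7. Other evidence on first-dose kinetics.** The QD cohorts (75, 125, 200 and 300 mg) have an uncontaminated 24 h sample. BID single doses are 100, 200, 300 and 400 mg. Two match a QD dose exactly, 100 mg lies between 75 and 125 mg, and only 400 mg is outside the QD range.

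**The case for a change.** The strongest case for a change is that an unwritten rule is not a prespecified one. The reviewed file contains no separate SAP, so nobody can confirm that the sample is handled properly. The table and plot in Section 12.6 are prescribed outputs and would carry the post-second-dose value with no analyst error. The cost would be one paragraph and a data flag, with no new samples.

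The timing fact stands, and so does the silence on the AUC interval and on the points for the terminal fit. The rest is weaker. A protocol's PK section is a summary, and its silence does not show that the working plan is silent too. The table and plot contain true values; they mislead only a reader who forgets that the cohort took two doses a day. The large multiples in half-life and AUC need a further step that the plan does not ask for and that a PK analyst with diary dose times would not take.

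Written text would not make the BID half-life much better either. With an assumed 20% assay error, a fit to 4, 6 and 8 h falls within 20% of the truth in only 26 to 68% of patients across the half-lives tried, at absorption rates of 0.8 and 1.5 per h. That limit comes from the sampling times.

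**Conclusion.** The observation is correct: in BID patients the 24 h sample at Phase 1 Cycle 1 Day 1 and Cycle 2 Day 1, and at Phase 2 Cycle 1 Day 1 if a BID dose is chosen, follows a second dose. It does not amount to an error in the plan, because no stated rule turns that sample into a wrong parameter. The possible distortion (half-life about 3.3 to 5.5 times true, first-dose AUC about 1.2 to 3.3 times) depends on a misuse that the plan does not prescribe and on assumed half-lives of 2 to 6 h. Ordinary handling brings both close to the truth.

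Little else depends on it. The maximum tolerated dose follows DLT counts (Section 6.1.1.3), Cmax and Tmax are untouched, and the QD cohorts give clean late samples over most of the single-dose range. The gap is one that analysts fill sensibly, and no change follows. The conclusion would differ if the separate SAP told analysts to treat the BID 24 h value as a first-dose point; nothing in the documents suggests that it does.
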